# Specific Aim 5. Androgen and neuroactive steroid levels will be lower in postmenopausal women with treatment resistant depression than in healthy controls.

We will investigate androgen and neuroactive steroid levels in postmenopausal women with treatment resistant depression in comparison to androgen and neuroactive steroid levels in postmenopausal healthy controls without significant psychiatric disease.

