- Currently treated with an antidepressant (1st, 2nd or 3rd trial in current episode), that has been taken at an adequate dose for at least eight weeks with sufficient source documentation to confirm high level of confidence in treatment details (using the MGH ATRQ). Current treatment may include a combination therapy as long as the subject has not exceeded three failed trials in the current episode.
- 5. Persistent depression symptom burden of the same dose of the currently (ineffective) antidepressant therapy, evidenced by MADRS≥12.

Exclusion Criteria for Randomized Study Subjects:

- 1. Serious suicide or homicide risk, as assessed by evaluating clinician
- 2. Unstable medical illness including cardiovascular, hepatic, renal, respiratory, endocrine, neurologic
- 3. Substance use disorder active within last six months, or clinical suspicion of ongoing substance use disorder at the discretion of the study clinician at time of screening based on history and/or laboratory results.
- 4. Any history of psychotic features, bipolar disorder, or primary obsessive compulsive disorder, as assessed by SCID
- 5. Untreated hypothyroidism. If treated hypothyroidism, change in levothyroxine dose within the prior 3 mos
- 6. Use of androgens, including testosterone, DHEA and methyltestosterone, within the prior three months
- 7. Any investigational psychotropic drug within the last 30 days
- 8. In the judgment of the study clinician, unlikely to be able to participate safely throughout the study period (three or more episodes of self-harm in the past year, documented history of poor treatment adherence, or frequent missed appointments (>50%) in the past year)
- 9. Alanine aminotransferase (ALT) > 3x upper limit of normal or creatinine> 3x upper limit
- 10. History of a hormone-responsive cancer
- 11. History of testosterone abuse
- 12. Almond allergy (AndroFeme contains almond oil)
- 13. History of hypercalcemia or thromboembolism
- 14. Women who are breastfeeding
- 15. Pregnant women, women who desire to become pregnant, or women of child bearing potential who are not using a medically accepted means of contraception (to include condom, diaphragm, spermicide, intrauterine device, tubal ligation, or partner with vasectomy)

Additional Exclusion Criteria for Randomized study subjects in fMRI Substudy Only (n=20)

Exclusion criteria for the fMRI substudy participants include routine MRI exclusion criteria as listed below:

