- Cardiac pacemaker
- Surgical aneurysm clips
- Neurostimulator
- Implanted pumps
- Metal fragments in body / eyes
- Pregnancy
- Nitroglycerin patch (if non-removable)
- Weight >250
- Severe claustrophobia

Healthy Control fMRI Population (n=20)

Inclusion criteria for fMRI Healthy Control Subjects

- Match a randomized subject based on:
  - $\circ$  Age (+/- 2 years)
  - $\circ$  BMI (+/- 2 kg/m^2)
  - Hormonal status

Exclusion criteria for fMRI Healthy Control Subjects

- Any history of psychiatric illness including major depressive disorder, bipolar disorder, psychotic features, or obsessive compulsive disorder, as assessed by SCID
- Current or prior use of any psychiatric medications
- Current or prior substance use disorder
- Unstable medical illness including cardiovascular, hepatic, renal, respiratory, endocrine, neurologic
- Hypothyroidism
- Use of androgens, including testosterone, DHEA and methyltestosterone, within the prior three months
- Abnormal alanine aminotransferase (ALT) or creatinine
- Women who are breastfeeding
- Pregnant women, women who desire to become pregnant, or women of child bearing potential who are not using a medically accepted means of contraception (to include condom, diaphragm, spermicide, intrauterine device, tubal ligation, or partner with vasectomy)
- Additional Routine MRI exclusion criteria as listed below:
  - Cardiac pacemaker
  - Surgical aneurysm clips
  - Neurostimulator
  - Implanted pumps
  - Metal fragments in body / eyes
  - Nitroglycerin patch (if non-removable)
  - Weight >250
  - Severe claustrophobia

Inclusion Criteria for Healthy Controls:

- 1. Female, age 50-75, who provide written informed consent
- 2. Free of lifetime psychiatric medication use
- 3. Postmenopausal, defined as amenorrhea for greater than one year and/or elevated FSH for women with prior hysterectomy

Exclusion Criteria for Healthy Controls:

- 1. Unstable medical illness including cardiovascular, hepatic, renal, respiratory, endocrine, neurologic
- 2. Current or past Axis I psychiatric or substance use disorder (non-prescribed medications, recreational drugs, or alcohol)
- 3. Use of androgens, including testosterone, DHEA and methyltestosterone, within the prior three months

Briefly describe study procedures. Include any local site restrictions, for example, "Subjects enrolled at Partners will not participate in the pharmacokinetic portion of the study." Describe study endpoints.

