# Baseline Visit for the Randomized, Placebo-Controlled, Augmentation Study: Eligible

subjects will undergo baseline testing immediately before the augmentation phase of the protocol. Baseline visit testing will include the following. However, the blood draw will not be repeated if the Baseline visit occurs within 2 weeks of the screening visit.

- Weight, vital signs, waist-to-hip ratio, and consumptive habits (alcohol, caffeinated beverages) will be recorded
- Urine pregnancy test (for premenopausal women only). Postmenopausal is defined as at least one year since last menses and FSH in the postmenopausal range
- Baseline endocrine blood testing: free testosterone, estradiol, neuroactive steroid panel, DHEAS, blood cortisol, late night salivary cortisol and 8 a.m. salivary cortisol
- o Baseline safety blood testing: ALT, creatinine, CBC
- Depression: MADRS, IDS-SR, CGI-I, S
- Cognitive Functioning: CPFQ
- o Persistent/residual symptom assessment: SF-36, BFI, ESS, FSS, DISF
- Safety assessments: SAFTEE-SI, CHRT, and hirsutism and skin assessments
- We will distribute the Study Drug Compliance and Hot Flash Diary or Menopausal Symptom Diary

• We will also collect DNA to be banked for a future exploratory study into whether androgen receptor CAG repeat length moderates androgen-behavior relationships (based on data by Seidmanet *et al.*).

**Follow-up Visits (Placebo-Controlled Augmentation Phase):** Subjects will then be randomized to receive low-dose testosterone or placebo. Follow-up visits will take place at weeks 2, 4, 6 and 8 post-baseline. Follow up visits will include:

- Urine pregnancy test (for premenopausal women only). Postmenopausal is defined as at least one year since last menses and FSH in the postmenopausal range (weeks 2, 4, 6 and 8)
- Free testosterone levels (weeks 2, 4, 6 and 8)
- Skin evaluations to monitor for side effects (weeks 4 and 8)
- Weight and vital signs will be recorded (weeks 4 and 8)
- Waist-to-hip ratio (week 8)
- Depression: MADRS, IDS-SR, CGI-I, S (weeks 2, 4, 6 and 8)
- Cognitive Functioning: CPFQ (weeks 2, 4, 6 and 8)
- Persistent/residual symptom assessment: SF-36, BFI, ESS, FSS, DISF (weeks 2, 4, 6 and 8)
- Safety: SAFTEE-SI, CHRT (weeks 2, 4, 6 and 8)
- Estradiol levels (weeks 2, 4, 6 and 8)
- Salivary cortisol (week 8)
- Medication management sessions (weeks 2, 4, 6 and 8)
- Neuroactive steroid panel (week 8)

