# Healthy control Visits

**Screening Visit (n=60):** A "Screening Visit" will be conducted to determine eligibility. It is estimated that 60 women will need to be screened to obtain 30 eligible study subjects.

The screening visit will include:

- Abbreviated SCID
- o Medical and psychiatric history including past psychiatric medication use

**Baseline Visit (n=30):** The baseline visit will occur if subjects are found eligible.

Baseline visit will include:

- Psychiatric assessments: MADRS, IDS-SR, CGI-I, S, CPFQ, SF-36, BFI, ESS, FSS, DISF, SAFTEE-SI, CHRT
- Height, weight, vital signs, waist-to-hip ratio, and consumptive habits (alcohol, caffeinated beverages) will be recorded
- Salivary cortisol
- Blood for androgens including total testosterone, free testosterone, neuroactive steroid levels, including allopregnanolone, and cortisol, and other hormones

Describe explicitly the methods for ensuring the safety of subjects. Provide objective criteria for removing a subject from the study, for example, objective criteria for worsening disease/lack of improvement and/or unacceptable adverse events. The inclusion of objective drop criteria is especially important in studies designed with placebo control groups.

**Suicide Prevention:** Suicidal ideation will be assessed by the Beck Suicide Index at each visit. Patients who develop active suicidal ideation, or who are felt by the study clinician to be at high risk for suicide, will be discontinued from the study and referred for hospitalization and further treatment if clinically indicated. In addition, each study subject will be extensively interviewed at each study visit by a highly trained psychiatrist, who not only has extensive experience in the treatment of major depression, but also with these issues in the setting of clinical trial protocols. Patients in research protocols have much more access to psychiatrists than patients in the community, as a study psychiatrist is available by pager 24 hours per day. Moreover, the studies are performed in hospitals in which patients can be immediately admitted, if necessary to ensure safety.

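### Aim 5 hormone comparison: ovarian status is recorded in neither group and hormone-responsive cancer is excluded on one side only, which could contribute to or mask a difference if the groups differ

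*Protocol*

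**What the plan says.** Specific Aim 5 of the Protocol states a directional hypothesis: "Androgen and neuroactive steroid levels will be lower in postmenopausal women with treatment resistant depression than in healthy controls". The comparison is between cohorts, and the outcome is the hormone level itself.

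- **Controls, menopause rule** (Inclusion Criteria for Healthy Controls, no. 3): "Postmenopausal, defined as amenorrhea for greater than one year and/or elevated FSH for women with prior hysterectomy". Age is 50-75. About 60 are screened to obtain 30.
- **Controls, exclusions** (Exclusion Criteria for Healthy Controls, nos. 1-3): no. 1 is "Unstable medical illness including cardiovascular, hepatic, renal, respiratory, endocrine, neurologic", no. 2 covers Axis I and substance use disorders, and no. 3 is "Use of androgens, including testosterone, DHEA and methyltestosterone, within the prior three months". Cancer history is not mentioned.
- **Depressed women, cancer rule** (Exclusion Criteria for Randomized Study Subjects, no. 10): "History of a hormone-responsive cancer".
- **Depressed women, menopause rule** (Baseline Visit, attached to the pregnancy-test item): "Postmenopausal is defined as at least one year since last menses and FSH in the postmenopausal range". Age is 21-75.
- **History taken**: a complete medical history at screening for randomized subjects, and for controls "Medical and psychiatric history including past psychiatric medication use".
- **Analysis**: the SAP covers Aims 1 to 3 only. It has no Aim 5 model and no Aim 5 covariates.

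Oophorectomy, ovarian status and surgical menopause appear in no eligibility list, visit list or model.

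**The concern.** Amenorrhea and a raised FSH show that a woman is postmenopausal. They do not show whether her ovaries are still present. If women without ovaries have lower androgen levels (a working assumption here, since the documents give no figure), then any gap between the groups in the share of such women appears as a gap in androgen level. An excess among depressed women would push the result towards the Aim 5 hypothesis, and an excess among controls would push it away. Randomization gives no protection, because this is not the randomized comparison.

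The cancer rule differs between groups by design. A control with a stable past hormone-responsive cancer, including one whose ovaries were removed for it or who takes endocrine therapy, meets the written criteria. A depressed woman with that history does not. What is at stake is how an Aim 5 difference, or its absence, can be read.

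**Working it through.** The plan states no alpha, power, SD, effect size or number of depressed postmenopausal women for Aim 5, so there is no figure to reproduce. The check has three parts. Only the 30 controls come from the documents; every other numerical input is an assumption.

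**1. Rules side by side**

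| Item | Depressed cohort | Aim 5 controls |
|---|---|---|
| Ovarian status | not addressed | not addressed |
| Hormone-responsive cancer | excluded | not excluded |
| Androgens in prior 3 months | excluded | excluded |
| Menopause rule | last menses and FSH | amenorrhea and/or FSH after hysterectomy |
| Age | 21-75 | 50-75 |
| Matching on hormonal status | none for Aim 5 | none (fMRI controls only) |

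The gap on ovarian status is the same in both groups. The gap on cancer history is on one side.

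**2. Ovarian status, log scale**

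Assumed: level 30-50% lower without ovaries; imbalance 10-20 percentage points; log SD 0.4-0.6; 30-50 cases; two-sided 5% test.

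- Bias = imbalance × −ln(1 − reduction)
- SE = SD × √(1/30 + 1/cases)
- Rejection with no depression effect = P(|Z + bias/SE| > 1.96)

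| | Bias | SE | Bias/SE | Rejection |
|---|---|---|---|---|
| Low (10 points, 30%, SD 0.6, 30 cases) | 0.1 × 0.357 = 0.036 | 0.155 | 0.23 | 5.6% |
| Midpoints (15 points, 40%, SD 0.5, 40 cases) | 0.15 × 0.511 = 0.077 | 0.121 | 0.63 | about 10% |
| High (20 points, 50%, SD 0.4, 50 cases) | 0.2 × 0.693 = 0.139 | 0.092 | 1.50 | 32% |

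On the original scale the bias is about 4% to 13% of the level. The top row of the range needs all four inputs at their extremes together.

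**3. Same question in SD units, including the added variance**

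Let g be the deficit without ovaries in within-stratum SDs, and pd and pc the shares without ovaries in depressed women and controls, with 30 women per group.

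- Bias = g × (pd − pc)
- SE² = [1 + g²·pc(1 − pc)]/30 + [1 + g²·pd(1 − pd)]/30

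Example: with g = 1, pd = 30% and pc = 10%, bias = 0.20, SE = √(1.09/30 + 1.21/30) = 0.277, and rejection is 11.2%.

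| pd / pc | Quantity | g = 0.5 | g = 1.0 | g = 1.5 |
|---|---|---|---|---|
| 20% / 20% | rejection, no true difference | 5% | 5% | 5% |
| 20% / 20% | power, true 0.7 SD difference | 76% | 71% | 64% |
| 30% / 10% | rejection, no true difference | 6.7% | 11.2% | 17.1% |
| 40% / 10% | rejection, no true difference | 8.8% | 19.0% | 31.9% |
| 10% / 30% | power, true 0.7 SD difference | 63% | 44% | 27% |

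Power for 0.7 SD is 77% when no woman in either group lacks ovaries. Equal shares therefore cost some power and cause no false rejection. Unequal shares act in the direction of the imbalance.

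**4. Endocrine therapy in controls**

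If a share q of controls is on therapy that shifts the level by h SDs, the control mean moves by q × h. For q = 3-10% and |h| = 0.5-1.0 this is 0.015 to 0.10 SD, which is smaller than most of the ovarian-status biases above (0.10 to 0.45 SD in the unequal rows of the table).

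**The case against.** The strongest reply is that ovarian status is unaddressed in both groups alike, so bias requires an imbalance that nothing in the documents demonstrates. That stands, and it is why the point is conditional. It does not remove the point, because nothing in the design makes the shares equal either: the age ranges, menopause definitions and cancer rules all differ.

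Second, the sizes rest on assumptions, and 32% is a corner value. That also stands; about 10% at midpoints is the fairer single illustration, and the low end is close to nominal.

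Third, the one rule that is truly asymmetric probably has a small effect. If it lowers control levels, it works against the hypothesis and cannot yield a false positive in the stated direction. It also does not make oophorectomy impossible among depressed women, since only hormone-responsive cancer is barred; ovaries removed for other reasons remain possible. Control exclusion no. 1 might catch some women under active treatment, though not a stable past cancer.

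Fourth, both groups already give a medical history. That makes the remedy cheap, but no rule records or uses ovarian status from it.

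A reader might go further and infer that these criteria do create the Aim 5 difference, or that they are what stands between Aim 5 and a conclusion about depression. The documents support neither. They give no prevalence and no effect size, and a different rule is likely to weigh more. Depressed women must have free testosterone at or below the third quartile of normal (Inclusion Criteria for Randomized Study Subjects, no. 2), and controls have no cap. If both populations follow a normal reference distribution on a suitable scale and the cap is its 75th percentile, truncation alone lowers the depressed mean by about 0.42 SD (remaining SD 0.73). With 30 per group that gives about 47% rejection with no true difference.

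**Conclusion.** The point holds in conditional form. In a non-randomized comparison of hormone levels, the plan does not establish ovarian status in either group and applies the hormone-responsive-cancer exclusion to depressed women only. This could contribute to or mask a difference if the groups differ in the share of women without ovaries or on endocrine cancer therapy; with equal shares it only adds variance.

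The size cannot be found from the documents. Under the assumed ranges, false rejection is about 6-32%, and about 10% at midpoints. This rests on lower androgen levels without ovaries, on a two-sided 5% test that the plan does not specify, and on the randomized cohort supplying the Aim 5 cases. That last assumption is reasonable, since it is the only depressed cohort described.

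Severity is minor: the randomized comparison and the MADRS primary endpoint are unaffected. Correcting this point alone would not make Aim 5 unbiased. The one-sided free-testosterone cap and the two differing postmenopausal definitions need separate handling.

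**What to change.** 1. In the medical history already taken at both screening visits, record prior bilateral oophorectomy as yes, no or unknown.
2. When an Aim 5 analysis is written into the SAP, compare log hormone levels with ovarian status as a covariate, and add a supporting analysis in women known to have their ovaries. Report the number in each category by group, so that any imbalance is visible.
3. Apply the same hormone-responsive-cancer criterion to both groups in the Aim 5 analysis set, for example by leaving controls with that history out of the analysis.

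The cost is one history question, one degree of freedom (two if unknown is kept as its own level) and possibly one or two controls. Going from 30 to 28 controls against 30 depressed women raises √(1/n₁ + 1/n₂) from 0.258 to 0.263, about 2% in the standard error. If few women lack ovaries, the adjusted estimate will lean on a small cell, and the ovary-intact analysis will be the easier one to read.

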# Study visits for randomized subjects

**Screening Visit:** A screening visit will take place to determine eligibility for enrollment. Participants will be asked to complete the MGH ATRQ and sign release of information forms to request documentation from prescribing clinicians. It is estimated that after review of detailed source documents describing past treatment details, 60 women will be confirmed to have partial/nonresponse to antidepressant therapy and be eligible for the randomized, placebo-controlled phase. Screening visit testing will include:

- o complete medical history
- o physical examination, including height and weight
- 0800h Blood draw for ALT, creatinine, CBC, thyroid stimulating hormone (TSH), free testosterone, FSH, urine pregnancy and toxicology
- o diagnostic interview with SCID
- MDD symptom assessment with MADRS
- completion of the MGH ATRQ

If antidepressant-resistance is confirmed following screening procedures, the subject will be scheduled for a baseline visit approximately 1-2 weeks.

# Baseline Visit for the Randomized, Placebo-Controlled, Augmentation Study: Eligible

subjects will undergo baseline testing immediately before the augmentation phase of the protocol. Baseline visit testing will include the following. However, the blood draw will not be repeated if the Baseline visit occurs within 2 weeks of the screening visit.

- Weight, vital signs, waist-to-hip ratio, and consumptive habits (alcohol, caffeinated beverages) will be recorded
- Urine pregnancy test (for premenopausal women only). Postmenopausal is defined as at least one year since last menses and FSH in the postmenopausal range
- Baseline endocrine blood testing: free testosterone, estradiol, neuroactive steroid panel, DHEAS, blood cortisol, late night salivary cortisol and 8 a.m. salivary cortisol
- o Baseline safety blood testing: ALT, creatinine, CBC
- Depression: MADRS, IDS-SR, CGI-I, S
- Cognitive Functioning: CPFQ
- o Persistent/residual symptom assessment: SF-36, BFI, ESS, FSS, DISF
- Safety assessments: SAFTEE-SI, CHRT, and hirsutism and skin assessments
- We will distribute the Study Drug Compliance and Hot Flash Diary or Menopausal Symptom Diary

• We will also collect DNA to be banked for a future exploratory study into whether androgen receptor CAG repeat length moderates androgen-behavior relationships (based on data by Seidmanet *et al.*).

**Follow-up Visits (Placebo-Controlled Augmentation Phase):** Subjects will then be randomized to receive low-dose testosterone or placebo. Follow-up visits will take place at weeks 2, 4, 6 and 8 post-baseline. Follow up visits will include:

- Urine pregnancy test (for premenopausal women only). Postmenopausal is defined as at least one year since last menses and FSH in the postmenopausal range (weeks 2, 4, 6 and 8)
- Free testosterone levels (weeks 2, 4, 6 and 8)
- Skin evaluations to monitor for side effects (weeks 4 and 8)
- Weight and vital signs will be recorded (weeks 4 and 8)
- Waist-to-hip ratio (week 8)
- Depression: MADRS, IDS-SR, CGI-I, S (weeks 2, 4, 6 and 8)
- Cognitive Functioning: CPFQ (weeks 2, 4, 6 and 8)
- Persistent/residual symptom assessment: SF-36, BFI, ESS, FSS, DISF (weeks 2, 4, 6 and 8)
- Safety: SAFTEE-SI, CHRT (weeks 2, 4, 6 and 8)
- Estradiol levels (weeks 2, 4, 6 and 8)
- Salivary cortisol (week 8)
- Medication management sessions (weeks 2, 4, 6 and 8)
- Neuroactive steroid panel (week 8)
- We will distribute the Study Drug Compliance and Hot Flash Diary or Menopausal Symptom Diary (weeks 2, 4, 6, and 8)

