Rigorous, randomized, placebo-controlled trials are necessary to determine whether lowdose testosterone augmentation will be an effective treatment for depression in women with inadequate response to antidepressant **therapy**. In this application, a double-blind, placebocontrolled trial of adjunctive low-dose testosterone for inadequate response to antidepressant **therapy** among MDD women is proposed.

*Specific Aim 1*. Low-dose testosterone augmentation improves depressive symptoms in women with MDD and partial/nonresponse to antidepressant therapy.

*Aim 1A.* We will investigate in female antidepressant therapy partial/nonresponders whether low-dose testosterone augmentation for 8 weeks leads to a significantly greater reduction in depressive symptoms than placebo.

*Aim 1B.* We will investigate whether a key mechanism underlying the effects of testosterone administration on depressive symptoms is an increase in neuroactive testosterone metabolites, including 3alpha-diol.

*Specific Aim 2.* Adjunctive low-dose testosterone is safe and well-tolerated in women with MDD and partial/nonresponse to antidepressant therapy. We will investigate whether low-dose testosterone augmentation therapy for 8 weeks is safe and well-tolerated in female antidepressant therapy partial/non-responders compared to placebo.

*Specific Aim 3.* Low-dose testosterone augmentation improves two specific RDoC construct symptoms (in the Arousal/Physiologic Processes Domain) in women: fatigue and sexual dysfunction. We will investigate in female antidepressant therapy partial/nonresponders whether low-dose testosterone augmentation for 8 weeks improves associated fatigue and sexual dysfunction compared to placebo.

*Specific Aim 4.* Low-dose testosterone therapy in women with treatment resistant depression will cause functional changes in the brain. We will investigate the mechanisms and functional neuroanatomy of the effects of testosterone on different regions of the brain in women with treatment resistant depression. This will serve as preliminary data for future studies and grants.

*Exploratory Aim:* We will investigate androgen and other hormonal correlates of functional and structural neuroanatomy in women with treatment resistant depression compared with healthy, non-depressed controls. This will serve as preliminary data for future studies.

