#### **RESEARCH DESIGN AND METHODS**

Briefly describe study design and anticipated enrollment, i.e., number of subjects to be enrolled by researchers study-wide and by Partners researchers. Provide a brief summary of the eligibility criteria (for example, age range, gender, medical condition). Include any local site restrictions, for example, "Enrollment at Partners will be limited to adults although the sponsor's protocol is open to both children and adults."

**Study Design:** After antidepressant therapy partial or nonresponse is established by documentation of failure to at least 8 weeks' treatment with an adequately dosed antidepressant therapy, A minimum of 100 subjects study-wide (60 from MGH) with MADRS $\geq$ 12 will enter the double-blind augmentation randomized-placebo-controlled treatment study. 50 of these subjects will be on active study drug and 50 will be control subjects on placebo. Eligible subjects will undergo baseline assessment of symptoms and biological measures and then be randomized to 1 of 2 groups: low-dose physiologic testosterone augmentation by transdermal preparation or placebo.

Antidepressant dose will be held steady during the trial. Outcome measures will examine the antidepressant efficacy of physiologic testosterone treatment (Aim 1), its tolerability (Aim 2) and its effects on 2 specific RDoC symptoms (Aim 3).

**Subject Enrollment:** A total of 330 women will be enrolled study-wide, of which 100 women with antidepressant-resistant MDD and 50 women with no psychiatric history will be eligible study-wide. Study subjects for the depressed population will be women, ages 21-75 with failure to remit following at least 8 weeks antidepressant trial documented by past treatment history.

In addition, 20 healthy controls without

depression will be recruited for the fMRI substudy healthy control population.

Up to 60 postmenopausal women who do not have current or past psychiatric disorders will also be screened to obtain 30 women who will be enrolled

as healthy controls.

Randomized Study Subject Population (n=60)

Inclusion Criteria for Randomized Study Subjects:

- 1. Female, age 21-75, who provide written informed consent
- 2. Free testosterone level no higher than the third quartile of the normal range
- 3. Meet DSM-IV criteria (by SCID) for current Major Depressive Disorder and have MADRS≥12

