Data Analysis: For Aim 1, the data will be analyzed using a mixed-effect linear regression model. The randomization will be stratified by site, estrogen use, and one vs. more than one adequate antidepressant therapy trial. The model will specify a baseline MADRS score and baseline non-responder vs. partial responder as covariates and then an "on treatment score," which is the score from weeks 2 through 8. The following will be entered into the model as covariates: baseline non-responder vs. partial responder, one vs. more than one adequate antidepressant therapy trial, baseline free testosterone level, baseline age and site (MGH or Butler Hospital). The on treatment score will have a fixed treatment effect and a random patient effect. We will examine interactions between menopausal status and effect to determine whether menopausal status moderates the treatment effect. This model is the same as in a repeated measures analysis of (co)variance with the assumption of compound symmetry. Our pilot data shown in Figure 2 fits this model. Specifically, based on our preliminary data, we expect a rapid improvement in depression severity by 2 weeks followed by maintenance of the effect of the subsequent 6 weeks. One advantage of this method is that it allows us to use data from patients who drop out early despite our plans to obtain follow-up data on all patients randomized and analyze all data obtained. A subject who drops out in the middle of the study will add data to the analysis. The drop-out rate should be low due to the relatively short duration of the study and the anticipated low side effect profile, the latter as confirmed in our pilot study in this population in which we had no drop-outs over the 8-week period. This model assumes that the drop-outs are missing at random. We will attempt to obtain 8-week observations on all patients, including drop-outs. Sensitivity analysis will be performed to determine whether our conclusions are sensitive to this assumption (185). Secondary analyses will determine whether the response of depressive symptoms to testosterone is affected by baseline androgens and neuroactive metabolites (including free testosterone level, DHEAS, and 3α -diol), estradiol, blood cortisol, late night cortisol and 8 a.m. salivary cortisol, and changes in the same variables over the 8-week period. Pre-treatment free testosterone level will be entered into the model as a covariate along with a treatment baseline interaction. Other covariates that will be explored will be age, menopausal status, baseline MADRS score, change in estradiol levels, change in free testosterone levels and BMI. As a secondary

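### In premenopausal women, estradiol and scan-day hormones are drawn by study week with no cycle date specified, so cycle phase is uncontrolled in the baseline-estradiol secondary analysis and the fMRI hormone correlates

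*Protocol*

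**What the plan says.** **Who is included.** The first inclusion criterion for randomized subjects is "Female, age 21-75, who provide written informed consent". The visit lists expect cycling women, since they include "Urine pregnancy test (for premenopausal women only". The number of premenopausal women is not stated. The contraceptive methods named as examples are non-hormonal apart from an unspecified intrauterine device, so natural cycling is plausible in many of these women.

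**When hormones are drawn.** The baseline panel is "Baseline endocrine blood testing: free testosterone, estradiol, neuroactive steroid panel, DHEAS, blood cortisol, late night salivary cortisol and 8 a.m. salivary cortisol". After that, "Follow-up visits will take place at weeks 2, 4, 6 and 8 post-baseline", and the follow-up list includes "Estradiol levels (weeks 2, 4, 6 and 8". Randomized women in the fMRI substudy are scanned at weeks 0 and 8 with a same-day hormone draw. Healthy fMRI controls receive one scan (the blood-draw line in their section also mentions an 8-week scan, which does not fit with that). Controls are matched on age, BMI and hormonal status; the last is not defined.

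**Use made of menstrual dates.** Last menses appears in the visit lists for randomized women only to classify them: "Postmenopausal is defined as at least one year since last menses and FSH in the postmenopausal range".

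**How the values are used.** SAP Specific Aim 1, Data Analysis, asks whether response is affected by baseline estradiol and by its change across the 8 weeks. It also lists among further covariates "baseline MADRS score, change in estradiol levels, change in free testosterone levels and BMI". The protocol's Exploratory Aim studies "androgen and other hormonal correlates of functional and structural neuroanatomy". Neither document has a cycle-phase term.

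**The concern.** In a naturally cycling woman, an estradiol value reflects both her usual level and the day of the cycle on which it was drawn. If the day is not known, the two cannot be separated later. A weak or absent relation between baseline estradiol and MADRS response would then be hard to read: estradiol may not matter, or the single value may be a poor measure of the woman's usual level.

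The fMRI hormone correlates have the same gap. The comparison with controls is the more exposed part, because each control is scanned once and nothing specifies that a control and her matched patient are at the same phase. At stake is the interpretability of secondary and exploratory results, not the trial's main conclusion.

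**Working it through.** The documents give no variance, power or precision figure for these analyses, so there is no stated number to reproduce. Two checks are possible.

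**1. Phase offset from a day-0 baseline (arithmetic on the visit weeks)**

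On an assumed 28-day cycle:
- Week 2: 14 mod 28 = 14 days. Week 6: 42 mod 28 = 14 days. Both are half a cycle out.
- Week 4: 28 mod 28 = 0. Week 8: 56 mod 28 = 0. Both are in phase.

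Week 8 with other cycle lengths:
- 26 days: 56 − 52 = +4 days.
- 30 days: 56 − 60 = −4 days.

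The SAP's change is over the 8 weeks, so week 8 is the relevant row.

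**2. Illustrative share of log-estradiol variance due to phase**

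Every input here is an assumption: log estradiol = woman's mean + sinusoidal phase + residual; peak-to-trough swing F of 2, 4 or 8; between-woman SD 0.3 or 0.5; residual SD 0.2 or 0.4. The sinusoid's amplitude is A = ln(F)/2.

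*Single draw.* Phase variance is A²/2 = (ln F)²/8, and share = phase variance / (phase variance + between-woman variance + residual variance). The non-phase variance runs from 0.09 + 0.04 = 0.13 to 0.25 + 0.16 = 0.41.
- F = 2: 0.060/(0.060 + 0.41) = 13% to 0.060/(0.060 + 0.13) = 32%.
- F = 4: 0.240/0.650 = 37% to 0.240/0.370 = 65%.
- F = 8: 0.541/0.951 = 57% to 0.541/0.671 = 81%.

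If response depends on a woman's usual level, the slope on one undated value keeps (1 − share) of its phase-free size, so from 1 − 0.13 = 87% down to 1 − 0.81 = 19%.

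*Week 0 to week 8 change.* For an offset of d days in a cycle of L days, phase adds variance A²(1 − cos(2πd/L)).
- In phase: 0.
- 4 days out: A²(1 − cos(2π·4/30)) = 0.33A² for a 30-day cycle; 0.43A² for 26 days.
- Offset spread evenly over 0 to 14 days in a 28-day cycle: the cosine averages to zero, giving A².
- Opposite phases: 2A².

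As a share of the change's variance (simulated for 200,000 women; the woman's mean cancels, so the denominator is phase plus twice the residual variance, with no genuine change included):

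| Swing | Exact 28-day cycles, same-day baseline | Cycle-length SD 2–4 days, same-day baseline | Baseline draw 0–14 days early, cycle-length SD 0–4 days |
|---|---|---|---|
| 2-fold | 0% | 11–54% | 25–60% |
| 4-fold | 0% | 34–83% | 57–86% |
| 8-fold | 0% | 53–92% | 75–93% |

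So the 8-week interval protects the change when cycles are close to 28 days and baseline is drawn on the day, and not otherwise.

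**3. Is baseline drawn on the day?** The Baseline Visit section says blood is not drawn again if baseline falls within 2 weeks of screening, and the Screening Visit section plans baseline about 1–2 weeks after. The screening panel is ALT, creatinine, CBC, TSH, free testosterone and FSH, with urine tests; estradiol is not on it. Read literally, baseline estradiol is missing for many women. If it were measured on the screening sample, it would be up to 14 days early, which is the last column of the table.

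**The case against.** The strongest reply is that the SAP's change covers 56 days, about two cycles, so a reader who infers that the change analysis compares opposite phases is looking at weeks 2 and 6, which are not the stated contrast. That stands, subject to the cycle-length and screening-draw limits above.

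Three further inferences go beyond the documents:
- *That these analyses mostly measure cycle phase.* No hormone variance and no count of premenopausal women is given. The share passes one half under some assumed inputs and not others. Estradiol is also measured at several visits, so the single-draw figures do not describe all the available data.
- *That all the hormones are affected alike.* Nothing in the documents shows phase dominating free testosterone, DHEAS, cortisol or the testosterone metabolites.
- *That the menopausal-status moderator test is compromised.* That test is an interaction with treatment in the MADRS model and uses no estradiol value.

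For imaging, it is fair to say that a same-day hormone level is real exposure on that day, so phase-driven differences are not simply error. That stands for a question about current level. It does not remove the possibility that phase confounds the correlates or the comparison with controls, which cannot be examined without a date.

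Finally, menstrual dates might be captured in the medical history or the symptom diary. The history is listed only at screening for randomized women and the diary's contents are not described. The accurate statement is that no date is specified, not that none will exist. Stratifying randomization by estrogen use does not address natural cycle phase.

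**Conclusion.** The point holds as a limited one. In premenopausal women, cycle phase is uncontrolled in the baseline-estradiol secondary analysis and in the exploratory fMRI hormone correlates, and as planned it could not be adjusted for afterwards. The 8-week estradiol change is less exposed, on condition of near-28-day cycles and a same-day baseline.

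The size cannot be derived from the documents; 13% to 81% for a single draw rests wholly on the assumed swings and standard deviations. The primary MADRS comparison uses no estradiol, and randomization balances phase between arms on average. The Aim 5 hormone comparison is confined to postmenopausal women and is also untouched. This is a cheap improvement to secondary and exploratory work, not a flaw in the main test.

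**What to change.** - **Protocol, Screening, Baseline and Follow-up Visits and both fMRI visit sections:** for premenopausal women, record the first day of last menses, usual cycle length and hormonal contraceptive use at each hormone draw and scan. This can be asked alongside the pregnancy test.
- **SAP, Specific Aim 1 secondary analyses:** add cycle phase as a covariate where estradiol is the explanatory variable, and report estradiol results separately for postmenopausal women.
- **fMRI hormone correlates:** use the same phase covariate, and define hormonal status for matching controls.
- **Baseline draw:** reconcile the rule against repeating the draw with the screening panel, so that it is clear whether baseline estradiol is measured and on which day.

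Cost: a short set of questions per visit, slightly more data entry and a few SAP lines. Phase will remain uncertain in women with irregular cycles, so the adjustment will be partial.
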